7.3 Analysis group

7.3.1 All subjects who complete visit 0 will be included in the analysis group.

7.4 Data analysis plan

7.4.1 A count of mild, moderate, and severe unique adverse events will be tallied from the data analysis set. The type of adverse event will also be tallied.

7.5 Success criteria

7.5.1 The absence of serious and related adverse events that could put the general population at risk.

\* Printed copies are uncontrolled unless otherwise identified \*

Before using this document, consult Grand Avenue to confirm current version before use.

CONFIDENTIAL

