17.0 Provisions to Monitor the Data to Ensure the Safety of Subjects

Data Analysis and Data Monitoring

This is a non-randomized, non-blinded, feasibility study involving a vaginal pessary. Given that the intervention is known to be safe and well-tolerated and the total exposure to our pessary for each subject was chosen to be similar to the typical interval of continuous pessary use which is common in clinical practice for current pessary users, we don't believe a formal data safety monitoring committee is required. However, a data and safety monitoring plan will be in place. The data safety monitoring plan will focus on low intensity monitoring by the Data Safety Monitoring Team, comprised of the one clinician from each participating site and a biostatistician. The Data Safety Monitoring Team will meet monthly, or sooner if necessary. Their charge will be to review subject accrual,

adherence to study protocol, and monitor adverse events. Additionally, they will ensure prompt reporting of serious adverse events to WCG IRB and the study sponsor (Reia, LLC).

At each contact with the subject, the clinical investigator will seek information on adverse events by specific questioning and by examination. Information on all adverse events will be recorded for review by the Data Safety Monitoring Team. Moderate adverse events which represent a change in baseline from those experienced in the washout period will be reviewed by the Data Safety Monitoring Team within one week. Serious adverse events, as defined by FDA criteria, will be reviewed by the Data Safety Monitoring Team within 24 hours and reported to WCG IRB and the study sponsor (Reia, LLC). Careful monitoring of the recruitment, enrollment, study procedures, and adverse events will help protect the safety of the subjects and quality of the data.

[figure not shown]
Any unanticipated adverse device effects that are possibly, probably, or definitely related to the study intervention will be immediately evaluated by the sponsor, Reia, LLC. If it is determined that the adverse device effect presents an unreasonable risk to the subjects, the investigation will be terminated within 5 working days of making the determination and not more than 15 working days of first receiving notice.

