**TITLE COLLAPSIBLE PESSARY FEASIBILITY TRIAL STATISTICAL ANALYSIS PLAN****5.0 RESPONSIBILITIES**

- 5.1 Reia personnel and approved suppliers will be responsible for analyzing data.
- 5.2 Reia must maintain all quality records, including copies of data analysis performed by approved suppliers, according to SOP-1002 Quality Records.

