7.2 Data collection method

7.2.1 At each visit, subjects will report discomfort, displacement, discharge, bleeding, obstructed urination, constipation, and other potential adverse events. If present, each reported event is described subjectively as mild, moderate, or severe by the subject.

7.2.2 At each in-person visit, practitioners will assess for physical exam findings of perineal tearing, vaginal irritation, vaginal ecchymosis, vaginal abrasions/superficial cuts, deep vaginal erosion, vaginal bleeding, granulation tissue, and copious vaginal discharge.

7.2.3 At each additional visit or phone call, expected and unexpected adverse events are reported by patients and/or observed by practitioners.

7.2.4 Study personnel can make entries in their site-specific F-3010 Trial Adverse Event Log for events described above or unique events not otherwise captured.

7.2.5 The events above will be reviewed and adapted to conform to Common Terminology Criteria for Adverse Events (CTCAE) ratings. The CTCAE ratings will be determined by the PI at each site.

7.2.6 The events will be condensed to unique adverse events consisting of:

- New subjective reports of events related to the study pessary not present at baseline with the current pessary
- Worsening subjective reports of events related to the study pessary that were present at baseline with the current pessary
- New physical exam findings related to the study pessary not present at baseline with the current pessary
- Worsening physical exam findings related to the study pessary that were present at baseline with the current pessary
- Any additional entries in the F-3010 Trial Adverse Event Log

These unique adverse events will represent the data analysis set.

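### The primary safety success rule (SAP 7.5.1) turns on an undefined population-risk clause, and the planned tally counts severity rather than seriousness

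*SAP*

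**What the plan says.** Adverse events are one of the two primary endpoints (Protocol 4.0; SAP 2.1). The relevant parts of the plan are these.

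- **Success rule, SAP 7.5.1:** "The absence of serious and related adverse events that could put the general population at risk".
- **Planned output, SAP 7.4.1:** "A count of mild, moderate, and severe unique adverse events will be tallied from the data analysis set". Event type is tallied as well. No other safety output is specified.
- **What enters the tally, SAP 7.2.6:** five categories. Four carry a relatedness condition, for example "New subjective reports of events related to the study pessary not present at baseline with the current pessary" and "Worsening physical exam findings related to the study pessary that were present at baseline with the current pessary". The fifth does not: "Any additional entries in the F-3010 Trial Adverse Event Log".
- **Grading, SAP 7.2.5:** "The CTCAE ratings will be determined by the PI at each site".
- **Seriousness, Protocol 17.0:** "Serious adverse events, as defined by FDA criteria, will be reviewed by the Data Safety Monitoring Team within 24 hours". These events also go to the IRB and the sponsor.
- **Relatedness scale and stopping, Protocol 17.0:** reporting uses a possible/probable/definite scale. Grade 4 and 5 events end the study even if their relation to the intervention is rated only unlikely.
- **Analysis responsibility, SAP 5.1:** "Reia personnel and approved suppliers will be responsible for analyzing data".

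**The concern.** A pass/fail rule for a primary safety endpoint should give one answer for one set of data. This rule has three conditions: serious, related, and capable of endangering the general population. The third narrows the first two, and nothing in either document says how it is to be met. An event that is serious and related, but held not to meet the third condition, leaves the endpoint a success. Two teams applying the rule in good faith to identical data could report opposite results, in a study that is single-arm and unblinded.

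The planned output does not settle the matter, because it reports severity while the rule turns on seriousness. The protocol treats these as different attributes: its definition of a severe event includes hospitalization only as a possibility (Protocol 4.0), whereas seriousness is set by separate FDA criteria (Protocol 17.0). A count of severe events therefore does not tell the reader whether a serious one occurred.

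**Working it through.** **1. Each condition of the rule against the documents**

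| Condition in 7.5.1 | Defined? | Who decides? | In the 7.4.1 tally? |
|---|---|---|---|
| Serious | Protocol 17.0, by FDA criteria; not cited in 7.5.1 | Reviewed by the Data Safety Monitoring Team; classifier not stated | No |
| Related | Scale in Protocol 17.0 for reporting; no scale or cut-off in the SAP | Not stated in the SAP | Not as a count; entry condition for 4 of 5 categories |
| Could endanger the general population | No | Not stated | No |

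The site PI's CTCAE rating is a severity grade, so it fills none of the empty cells. The tally has three severity levels, while Protocol 17.0 uses five grades; Grades 4 and 5 have no row of their own.

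**2. A case followed through**

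Suppose one Grade 3 event is classed as serious and rated probably related.

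- Protocol 17.0: reviewed within 24 hours and reported. The Grade 4/5 termination rule does not apply.
- SAP 7.4.1: adds one to the severe count and one to its type.
- SAP 7.5.1: failure if someone holds that it could endanger the general population, success if not. The documents supply no basis for choosing.

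For a Grade 4 or 5 event the study ends, but no text says that termination counts as failure under 7.5.1.

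**3. Size, as illustration only**

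There is no plan figure to reproduce: SAP section 7 gives no rate, error level or power, and the only power statement (Protocol 6.0) concerns the PFDI-20.

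Inputs:
- n = 40 (expected completers) or 50 (minimum enrolled), Protocol 6.0.
- p = true probability that a woman has a serious related event. Not in the documents; assumed 1% to 5%.
- q = share of such events held to meet the population-risk clause. Not in the documents; shown at 0.5, with the extremes 0 and 1.

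Formulas, assuming independent women and at most one such event each:
- No serious related event (the rule without the clause passes): (1 − p)^n
- Rule as written passes: (1 − pq)^n
- At least one serious related event and success still declared: (1 − pq)^n − (1 − p)^n

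| n | p | (1 − p)^n | (1 − 0.5p)^n | Difference |
|---|---|---|---|---|
| 40 | 1% | 0.6690 | 0.8183 | 0.149 |
| 40 | 2% | 0.4457 | 0.6690 | 0.223 |
| 40 | 5% | 0.1285 | 0.3632 | 0.235 |
| 50 | 1% | 0.6050 | 0.7783 | 0.173 |
| 50 | 2% | 0.3642 | 0.6050 | 0.241 |
| 50 | 5% | 0.0769 | 0.2820 | 0.205 |

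At q = 1 the difference is 0. At q = 0 with n = 50 it is 0.395, 0.636 and 0.923 for p = 1%, 2% and 5%. Given exactly one such event, the probability of success is simply 1 − q, so the result depends on a quantity the plan leaves open. These figures ignore the Grade 4/5 termination rule, so they overstate the effect to the extent that serious events reach those grades.

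**The case against.** The strongest reply is that the protocol already guards against what matters. Serious events are reviewed within 24 hours and reported to the IRB, and any Grade 4 or 5 event, even one thought unlikely to be related, ends the study. This stands in part: it narrows the practical gap mainly to serious related events below Grade 4. It does not close the gap, because these provisions govern reporting and conduct, and neither is tied to 7.5.1.

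Several stronger readings are tempting, and the documents do not support them.

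- *The tally ignores relatedness.* It does not: 7.2.6 makes relatedness an entry condition for four of the five categories. What is missing is a tabulation, a scale, a cut-off, and any such condition for F-3010 log entries.
- *The sponsor's analysts decide which events count.* SAP 5.1 assigns data analysis, not event classification. That nobody is named for the clause is a gap; it does not show that the analysts fill it.
- *The rule cannot be evaluated at all.* Serious events are identified outside the tally, and the data collection form and event log, which are not among the documents, may hold seriousness or causality fields. The supportable point is that 7.4.1 does not tabulate seriousness.
- *The rule names the wrong population.* The phrase can be read as future users beyond the trial, so nothing here rests on it.
- *The sample is too small for a zero-event rule.* Wide bounds after zero events apply to any such rule at 40 or 50 women, including one without the clause. They do not measure this defect.

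It may also be said that this is a feasibility study seeking preliminary data. That bears on how much weight the result can carry, not on whether the stated rule should give a determinate answer.

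**Conclusion.** The point holds in a limited form. As written, 7.5.1 permits success after a serious event related to the study pessary, because its last clause has no definition, threshold or decision-maker. The planned tally does not show seriousness, and relatedness acts only as a partial entry filter. This goes beyond missing detail, since identical data can yield either result on a primary endpoint.

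A reader might infer that any event whatever could be explained away. The documents do not go that far: Grade 4 and 5 events end the study, and serious events are reviewed and reported whatever the SAP says. The exposed range is mainly serious related events below Grade 4, plus the unstated standing of a terminated study under 7.5.1.

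The size cannot be derived from the documents. The figures of 0.15 to 0.24 rest on an assumed event rate of 1% to 5%, an assumed half of events set aside, and no allowance for the termination rule. The textual finding does not depend on them.

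**What to change.** 1. **SAP 7.5.1.** Delete the population-risk clause. If it is kept, define it and name, before analysis, who decides it; this should not be the data analysts. State that serious means the FDA criteria referred to in Protocol 17.0. Fix the relatedness cut-off in advance on the protocol's existing scale. The documents do not dictate where the cut-off falls, so the sponsor should choose and record it.
2. **SAP 7.4.1.** Add a listing and count of every event by seriousness, relatedness and all CTCAE grades, including 4 and 5. Say how a study termination under Protocol 17.0 is counted under 7.5.1. Without this, a Grade 4 event rated unlikely to be related could end the study and still leave the endpoint a success.
3. **Leave unchanged** the analysis group in SAP 7.3.1 and the charge of the Data Safety Monitoring Team. Neither needs to move to repair this rule.

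Cost: SAP wording and one added listing. If the event log or data collection form lacks fields for seriousness or relatedness, those would have to be added; the documents available do not show whether they exist. The downside is that the sponsor loses discretion to discount an event.

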## TITLE COLLAPSIBLE PESSARY FEASIBILITY TRIAL STATISTICAL ANALYSIS PLAN

**8.0 ADDITIONAL QUESTIONNAIRES (SECONDARY)**

8.1 Endpoint

- 8.1.1 Pelvic Floor Impact Questionnaire (PFIQ-7) of study pessary compared to current pessary
- 8.1.2 Pelvic Organ Prolapse/Urinary Incontinence Sexual Survey (PISQ-IR) of study pessary compared to current pessary

8.2 Data collection method

- 8.2.1 PFIQ-7 is a health-related quality of life instrument, designed to assess the life impact of pelvic floor symptoms in women with pelvic floor disorders. The PFIQ-7 has a parallel structure to the PFDI with 3 Scales: Colorectal Anal Impact Questionnaire (CRAIQ), Pelvic Organ Prolapse Impact Questionnaire (POPIQ), and Incontinence Impact Questionnaire (IIQ).
- 8.2.2 PISQ-IR is a validated evaluation tool which can be used clinically as well as in research for assessment of female sexual function (FSF) in women with female pelvic floor disorders.

8.3 Analysis group

- 8.3.1 PFIQ-7 and PISQ-IR are recorded at visit 0 for the current pessary and visit 3 for the study pessary, so only subjects who complete data collections forms through visit 3 will be included in the analysis.

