6.0 Procedures Involved

Methods

This is a non-randomized prospective trial. Treatment intervention will be non-blinded to the subject and the investigator. Subjects will serve as their own controls and enter the treatment phase of the study after a 1-month washout period of using their current pessary. Subjects will be recruited for this study from panels of patients in clinical practices specializing in Female Pelvic Medicine and Reconstructive Surgery (FPMRS). Inclusion will be based on pre-defined criteria outlined in "10.0 Inclusion and Exclusion Criteria."

The primary outcome measure will be the change in the scores of the Pelvic Floor Distress Inventory-20 (PFDI-20), administered first during the washout period while still using their current pessary and then at the conclusion of the treatment phase with the study pessary. The PFDI-20 is a validated health-related quality of life instrument to assess the *presence and bother of symptoms* in women with pelvic floor dysfunction. For women with relatively mild pelvic floor symptoms, a minimal important change (MIC) of between 13.5 and 18.3 points in the PFDI-20 score can be considered clinically relevant. At least fifty subjects will be enrolled, expecting that after drop-out and attrition at least 40 subjects will have completed the study. This provides power of .80 for a MIC equivalence limit of 17 points on the PFDI-20 scale.

There will not be discrimination based on race or ethnicity. It is anticipated that most participants will be post-menopausal as this reflects the demographic of women who suffer from this disorder.

The study will take place over 4 visits (Visit 0, Visit 1, Visit 2, and Visit 3).

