Visit 3 [research purposes] will occur at the conclusion of the 3-month (from Visit 1) treatment phase - a typical length of time between routine visits for patients who choose long term pessary management of their prolapse. It can be scheduled in a window between 11 and 13 weeks from Visit 1. When the subject returns for Visit 3, a physical exam will be repeated, as in previous visits, for comparative data. The study pessary will be observed in situ for the presence of rotation and its ability to support prolapse by measuring the distance of the most dependent compartment of the subject's prolapse to the hymen (Points Ba and Bp), as well as the distance from the leading edge of the study pessary to the hymen. A VAS will be used to assess discomfort with removal of the study pessary, discomfort with reinsertion of their current pessary, and their global satisfaction of the study pessary. The subject will have been instructed to return with their current pessary which was removed in Visit 1. If the subject's current pessary is not brought to the visit, they will be given a new pessary of the size and style of their current pessary. Each subject will complete the PFDI-20, PFIQ-7, and PISQ-R for a post treatment comparison. For self-managers, other data collected will include frequency of removal and a VAS for ease of study pessary insertion and removal.

Additional Visits: Subjects will be seen as necessary and adverse events will be managed according to standard of care. If the study pessary falls out after Visit 1, the subject may be seen at their convenience for reinsertion or resizing. If a study pessary cannot be fit and retained, the subject will be withdrawn from the study and their current pessary will be placed. If the subject's current pessary is not brought to the visit, they will be given a new pessary of the size and style of their current pessary.

Special Circumstances: If a subject dies between Visit 1 and Visit 3, an attempt will be made to contact the coroner to retrieve the study pessary. If the study pessary cannot be retrieved, a copy of the death certificate will be obtained.

The study pessary is the only device that will be used in this trial. There will be no placebo devices placed. The study pessary is not cleared by the FDA, and a rationale is provided for a non-significant risk device claim in the attached documents.

Data Collected

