13.0 Withdrawal of Subjects

Reasons for a subject to be withdrawn from the research study include:

- The subject is found to have a condition that does not allow participation in the research, such as a finding upon physical examination that excludes them from the study.
- The subject no longer tolerates their current pessary during the washout period or needs a different size or type of pessary during the washout period.
- The subject is not able to be fit with a study pessary at the conclusion of Visit 2, or the study pessary is repeatedly expelled.
- The study pessary causes discomfort or adverse reaction for which continued use is contraindicated.
- The subject has a reaction that requires immediate removal of the study pessary.
- The subject may withdraw themselves at any point for unforeseen circumstances.

DELA	DOCUMENT NUMBER	CP-002-01	r 03	
REIA		PAGE 16 OF 23		
TITLE COLLAPSIBLE PESSARY FEASIBILITY TRIAL PROTOCOL				

If a subject is removed from the study, already collected data may not be removed from the study database and will be handled with the same protocol as research data. The subject will receive the usual ongoing care for their pessary.

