8.5 Reportable outcomes

- 8.5.1 Average and standard deviation of the PFIQ-7 and PISQ-IR for the current and study pessary will be reported.
- 8.5.2 We will use a two-tailed t-test to test the null hypothesis that the mean difference score between baseline (current pessary) and study pessary on the PFIQ-7 is zero. This test is equivalent to a matched samples t-test. The p-value will be reported.
- 8.5.3 We will use a two-tailed t-test to test the null hypothesis that the mean difference between baseline (current pessary) and study pessary on the PISQ-IR is zero. This test is equivalent to a matched samples t-test. The p-value will be reported.

\* Printed copies are uncontrolled unless otherwise identified \*

Before using this document, consult Grand Avenue to confirm current version before use.

CONFIDENTIAL

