## TITLE COLLAPSIBLE PESSARY FEASIBILITY TRIAL STATISTICAL ANALYSIS PLAN

**10.0 GLOBAL SATISFACTION (SECONDARY)**

- 10.1 Endpoint
  - 10.1.1 Global assessment of study pessary satisfaction compared to current pessary
  - 10.1.2 Global assessment of study pessary satisfaction
- 10.2 Data collection method
  - 10.2.1 Satisfaction will be assessed using a Visual Analog Scale (VAS) with a 10 cm linear continuum in which 0 represents no satisfaction and 10 represents complete satisfaction.
- 10.3 Analysis group
  - 10.3.1 Global satisfaction is recorded at visit 1 for the current pessary and visit 3 for the study pessary, so only subjects who complete data collections forms through visit 3, or provide a score for both the current and study pessary before exiting the study, will be included in the analysis.
- 10.4 Data analysis plan
  - 10.4.1 For each subject, a difference (current pessary – study pessary) in satisfaction scores will be calculated.
- 10.5 Reportable outcomes
  - 10.5.1 Average and standard deviation of the global satisfaction of current and study pessary will be reported.
  - 10.5.2 Mean difference (current pessary – study pessary) in satisfaction scores will be reported.
  - 10.5.3 We will use a two-tailed t-test to test the null hypothesis that the mean difference score between baseline (current pessary) and study pessary for global satisfaction is zero. This test is equivalent to a matched samples t-test. The p-value will be reported.
  - 10.5.4 Cundiff et al. dichotomized VAS scores for pessary satisfaction into high satisfaction (greater than or equal to 80 mm) and low satisfaction (less than 80 mm). For this study, we similarly deemed a VAS of 80 mm would indicate high satisfaction. We will use a one-sided t-test to test the null hypothesis that the mean global satisfaction score for the study pessary is less than 80 mm. The p-value will be reported.

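### PFIQ-7 and PISQ-IR are analysed only in women who reach Visit 3, so these two comparisons describe women who kept the study pessary and use a different population from the primary PFDI-20 analysis

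*SAP*

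**What the plan says.** SAP 8.3.1 sets the analysis group for both questionnaires: "so only subjects who complete data collections forms through visit 3 will be included in the analysis". SAP 8.4 and 8.5 add a within-subject difference, means and standard deviations, and a paired test. The test sentence for PFIQ-7 begins "We will use a two-tailed t-test to test the null hypothesis that the mean difference score between baseline (current pessary) and study pessary on the", with zero as the null value, and PISQ-IR is tested in the same way. Section 8 has no second analysis set, exit score, imputation or sensitivity analysis.

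Protocol 6.0 places the study-pessary questionnaires at Visit 3: "Each subject will complete the PFDI-20, PFIQ-7, and PISQ-R for a post treatment comparison". It describes none at withdrawal.

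Protocol 6.0 also states: "If a study pessary cannot be fit and retained, the subject will be withdrawn from the study and their current pessary will be placed". Protocol 13.0 lists six withdrawal reasons, one of which is "The study pessary causes discomfort or adverse reaction for which continued use is contraindicated". On numbers, protocol 6.0 says: "At least fifty subjects will be enrolled, expecting that after drop-out and attrition at least 40 subjects will have completed the study".

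Other endpoints are handled differently. SAP 6.3.1 keeps PFDI-20 dropouts after Visit 1 with an assigned worse-limit score, and 6.3.2 adds a per-protocol analysis. SAP 10.3.1 admits satisfaction scores from women who complete through Visit 3 "or provide a score for both the current and study pessary before exiting the study".

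**The concern.** Whether a woman has a PFIQ-7 or PISQ-IR score on the study pessary depends partly on how the pessary performed. Those it failed leave before the only measurement. A mean change among those who remain answers a narrower question than how women given this pessary fare, and probably gives a more favourable answer.

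The SAP deals with the same problem for PFDI-20 and for satisfaction, but not here. SAP 8.2.1 describes PFIQ-7 as parallel in structure to the PFDI, so readers will set the two results side by side although they come from different populations. What is at stake is the interpretation of two secondary endpoints, not the primary conclusion.

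**Working it through.** **Figures in the plan.** Section 8 states no sample size or power, so it has no figure to reproduce. The only power statement concerns PFDI-20: "This provides power of .80 for a MIC equivalence limit of 17 points on the PFDI-20 scale". It gives no standard deviation. With 40 women and two one-sided tests at 0.05, a power of 0.80 implies an SD of the difference of about 36.7 points (normal form) or 36.1 (t-based), taking a true difference of zero. This does not bear on section 8.

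**How many may be missing.** Protocol 6.0 expects at least 50 enrolled and at least 40 completing. 50 − 40 = 10, and 10/50 = 20%; conversely 40/(1 − 0.20) = 50. The loss is counted from enrolment at Visit 0. It therefore includes women who leave during the washout, before the study pessary is tried at Visit 1. The documents do not split it by time or reason.

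**Which withdrawals relate to the device.** The six reasons in protocol 13.0 are:

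| Reason | Study-pessary failure? | Possible after Visit 1? |
|---|---|---|
| Excluding condition found | No | Yes |
| Current pessary not tolerated or changed in washout | No | No |
| Cannot be fit, or repeated expulsion | Yes | Yes |
| Discomfort or adverse reaction | Yes | Yes |
| Reaction needing immediate removal | Yes | Yes |
| Subject's own decision | No | Yes |

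That is three of six overall, and three of the five that can apply after Visit 1.

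**Shift in the mean, PFIQ-7 points.** Let m women without a score be d points worse than 40 completers whose mean change is 0. The mean over all Visit 1 completers then differs from the completer mean by m × d/(40 + m). The values of d, and the split of 5 and 5, are assumptions.

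| d | m = 10 (all leave after Visit 1) | m = 5 (the other 5 leave earlier) |
|---|---|---|
| 10 | 100/50 = 2.0 | 50/45 = 1.1 |
| 20 | 200/50 = 4.0 | 100/45 = 2.2 |
| 40 | 400/50 = 8.0 | 200/45 = 4.4 |

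The m = 10 column is the ceiling when exactly 50 enrol and 40 complete.

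**Effect on the test.** The documents give no PFIQ-7 or PISQ-IR standard deviation, so this step uses SD units of the paired difference. It assumes a within-group SD of 1 and two-sided alpha 0.05 (section 8 states no alpha). With 40 completers, p = 0.05 is reached at a mean of 2.023/√40 = 0.32 SD, and power is 80% at about 0.45 SD. A completer benefit of 0.45 SD gives t = 0.45 × √40 = 2.85 and p = 0.007. Adding the missing women gives:

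| Mean change in missing women | p, m = 10 | p, m = 5 |
|---|---|---|
| 0 | 0.015 | 0.010 |
| −0.5 SD | 0.09 | 0.03 |
| −1 SD | 0.33 | 0.08 |

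With m = 10, p crosses 0.05 when the missing women average about −0.32 SD.

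**The case against.** The strongest reply concerns the question being asked. Protocol 3.0 says a pessary works only while in place, and a woman who cannot be fitted has her current pessary put back. Followed to Week 16 on that pessary, she might score near baseline. Change among women still wearing the device is a legitimate secondary question, and 8.3.1 says openly that only completers are used. This stands as a reason to include zero in any sensitivity range. It does not remove the selection: with 10 missing women at zero, a completer benefit of 0.45 SD becomes 40 × 0.45/50 = 0.36 SD.

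It is also fair that failures appear elsewhere: fit and retention failures in SAP section 12, adverse events in section 7, and dropouts after Visit 1 in the PFDI-20 analysis. Unlike 6.5 and 7.5, section 8 has no success criterion, and protocol 2.0 says the study seeks preliminary data. All of this lowers the consequence.

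A reader might infer more than the documents support:

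- That most listed withdrawal reasons are device failures. It is three of six, a majority only after Visit 1, and no frequencies are given.
- That 50 is the number of women fitted. It is the number enrolled, before the washout.
- That bias towards the device is established. It is plausible, not shown.
- That the trial's quality-of-life results as a whole leave out failures. PFDI-20, which the protocol also calls a quality-of-life instrument, keeps dropouts after Visit 1.

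**Conclusion.** The point holds for PFIQ-7 and PISQ-IR. The completers-only rule is a stated choice, and it gives a selected result that probably favours the study pessary and does not share the primary analysis population. Up to 10 of 50 women may be absent. The PFIQ-7 shift is at most 2, 4 or 8 points for assumed gaps of 10, 20 or 40, and roughly half that if 5 of the 10 leave before Visit 1. The documents give no important change for PFIQ-7 against which to judge those points, and no basis for a PISQ-IR figure in points. In SD terms, plausible assumptions can move a nominally significant result past 0.05.

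The data collection form (CP-002-03) is not among the documents, so it may contain an exit questionnaire. Under 8.3.1 those scores would still be left out. The change should be made, but no trial success criterion depends on it.

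**What to change.** 1. In SAP 8.3.1, adopt the 10.3.1 rule, so that a study-pessary score given before leaving the study is included alongside the baseline score.
2. Amend the protocol and the data collection form so that women who have worn the study pessary complete both questionnaires at the withdrawal visit where feasible. SAP wording alone cannot create these data. No withdrawal or removal rule needs to change.
3. Label the Visit 3 result as completers only, and report the number excluded and the reasons, split before and after Visit 1.
4. Add one sensitivity analysis over all Visit 1 completers. Give those without a score a range of changes from zero to a stated worsening, set separately for each scale. Do not reuse the PFDI-20 value of 18.3.

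The cost is a protocol and form amendment, two questionnaires at a withdrawal visit, and a short SAP revision. There are three downsides: exit scores come after varying wear time, women never fitted have no study-pessary experience to score, and the range is an assumption. If enrolment has closed, items 3 and 4 need no new data, and item 1 can use any exit scores already held.
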